5.1.1 General study level definitions

Analysis Time Points

5.1.1.1.1 **Relative day**

Relative day will be calculated as the algorithm below:

If the event occurred on or after the date of first study drug administration, then the following calculation is used:

Relative $Day = Date_{event} - Date of first dose + 1$

Bimekizumab

If the event occurred before the date of first study drug administration, then the following calculation is used:

Relative
$$Day = Date_{event} - Date of first dose$$

oilation Relative days that occur before the date of first study drug administration will be preceded by a "-", when present in listings.

If the event occurred after the date of last study drug administration, then the following calculation is used:

```
Relative Day = Date_{event} - Date of last dose
```

Relative days that occur after the date of last study drug administration will be preceded by a "+", when present in listings.

Relative day will only be computed for fully completed dates and will be missing for partial dates.

5.1.1.1.2 End date of the Treatment Period

The end date of the Treatment Period will be either the date of Week 16 visit for study participants completing the Treatment Period, or the date of the PEOT for study participants who discontinued during the Treatment Period. If a study participant does not have a Week 16 visit/PEOT, then either the date of the last scheduled or unscheduled visit during the Treatment Period or the date of last known dose of study drug during the Treatment Period, whichever is later, will define the end date of the Treatment Period.

Study periods 5.1.1.1.3

The study consists of the following periods:

- Screening Period: the Screening Period will last 2 weeks, but can be extended up to a total • of 5 weeks in cases where a laboratory assessment needs to be repeated or to allow washout of prohibited medications. The Screening Period starts from the ICF date and ends one day before the first IMP administration date.
- Treatment Period: the Treatment Period starts from the date of first IMP administration and • ends at the Week 16 visit date or PEOT date.
- SFU Period: Only applicable to the study participants not entering the MAP. The SFU • starts one day after the end date of Treatment Period (Week 16 date or PEOT date) and ends at the SFU Visit (scheduled to be 20 weeks from final dose of IMP).

SFU data will be listed only, with the exception of the figures of ALT/AST values for participants with at least one markedly abnormal value and the inclusion of AEs with onset during the SFU period, which will be included in selected summaries, detailed in section 5.6.2.2.

A study participant will be considered to have completed a period if they complete the last scheduled study visit for that period.

5.1.1.1.4 Mapping of assessments performed at Early Discontinuation Visit

If the PEOT visit occurs at a scheduled visit as outlined in the schedule of assessments, then no mapping is necessary, and any PEOT assessments should correspond to that scheduled visit.

Bimekizumab

Premature study withdrawal visit assessments that occur on a date after a scheduled visit will be assigned to the next scheduled site visit per the protocol following the last visit where assessments were available. This approach means that there is a chance that data will be mapped to a visit where a given assessment was not actually collected per the protocol schedule of assessments. Such data will not be summarized in by-visit tables (though it will be available in the listings).

The only exception to the above rule is for anti-bimekizumab antibody assessments, in which all early withdrawal visit assessments will be assigned to the next scheduled visit at which antibimekizumab antibodies are assessed. The rationale for this is that anti-bimekizumab antibody positivity is summarized over a given study period. As part of that summary, a table indicating the first visit at which anti-bimekizumab antibody positivity is observed will be prepared. In order to match the number of study participants who were anti-bimekizumab antibody positive at specific visits with the overall positivity for the period, it is necessary to ensure that anti-bimekizumab antibody positivity is attributed to a visit where such assessments were performed.

All by-visit summaries will contain nominal visits only. Unscheduled visits will not be mapped to scheduled visits. However, in cases where vendor data is assigned to an unscheduled visit instead of a scheduled visit, the assessments will be mapped into the scheduled visit if the assessment dates fall into the permissible window, as detailed in section 5.1.

Note that based on the early withdrawal mapping conventions described above, a mapped early withdrawal visit is considered as observed at that visit and should be summarized as such in the tables.

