7.1.3 Treatment interruptions/temporary discontinuation of IMP

Doses of IMP that were missed due to a reasonable interfering AE or exceptional circumstance, which do not allow administration of IMP due to safety reasons, will not result in the study participant being considered noncompliant. The AE or exceptional circumstance should be discussed immediately with the Medical Monitor.

Any considerations related to restarting IMP should be discussed with the Medical Monitor.

The Investigator should not deviate from the protocol. However, the Investigator should take any measure necessary in deviation from, or not defined by, the protocol in order to protect clinical study participants from any immediate hazard to their health and safety. In this case, this action should be taken immediately, without prior notification of the regulatory authority, IRB/IEC, or Sponsor.

After implementation of such measure, the Investigator must notify the CPM of the Sponsor within 24 hours and follow any local regulatory requirements.

Any participant who develops a clinically important infection or recurrent infection not responsive to standard therapy during the study must discontinue IMP until resolution of the infection. The Investigator should use clinical judgement in deciding whether the participant should restart IMP, and contact the Medical Monitor and UCB study physician to confirm the participant's suitability for continued participation in the study.

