# 5.7.1 Other endpoints and/or parameters

# 5.7.1.1 Pharmacokinetics

Pharmacokinetic variables will be analyzed for all study participants in the PK-PPS who are treated with bimekizumab.

All plasma concentration data will be reported in ug/mL in the tables, figures, and listings. If the dosing for a visit is +/- 21 days out of window then the plasma concentration from that visit and all subsequent visits will be excluded from PK summaries.

If the PK sampling date is >1 day after the dosing date the data point will be excluded from the PK summaries.

All PK concentrations will be listed.

No imputation will be used for missing samples. However, plasma concentrations below the limit of quantification (BLQ) will be set to  $\frac{1}{2}$  of LLOQ in the calculation of the derived statistics (which will include number of values, geometric mean & its 95% CI, geometric coefficient of variation, mean, SD, median, minimum, and maximum). Geometric mean and its 95% CI, geometric CV, mean and SD will be calculated if at least  $\frac{2}{3}$  of the values of interest is above the LLOQ and n>=3; otherwise, only number of values, median, minimum, and maximum will be presented.

All concentrations obtained at the SFU visit will be listed only.

The geometric mean of bimekizumab plasma concentration (with 95% CI) time curve will be plotted on linear and semi-logarithmic scales. The table summary and figure will be repeated by anti-bimekizumab antibody status (positive, negative, missing). The missing group will not be displayed if <5% of study participants are categorized in the missing group.

The ADAb status (positive, negative, or missing) will be considered in a cumulative manner at each time point:

- A study participant will be counted as positive from the first visit at which the study participant achieved a positive ADAb sample result to the end of the treatment period (regardless of any missing/inconclusive or negative ADAb sample result).

- If a study participant has only negative ADAb samples or only one missing/inconclusive sample with negative ADAb samples up to that timepoint, the study participant will be classified as negative.

- Otherwise, the study participant will be classified in the missing ADAb category.

The table summary and figure will also be repeated by neutralizing anti-bimekizumab antibodies (NAb) status: (ADAb negative, NAb positive, ADAb positive/NAb negative, missing; section 5.7.2).

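### Plasma concentrations from premature-end-of-treatment visits after Week 2 enter the by-visit PK summaries under the next visit's label, whatever the time since the last dose

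*SAP*

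**What the plan says.** The schedule in Protocol Table 1-1 draws PK at Baseline, Weeks 4, 8 and 12, Week 16/PEOT and safety follow-up, before any dose given at that visit. SAP 6.1.10 gives the dosing visits as Baseline and Weeks 4, 8 and 12. There is no dose at Week 16 or PEOT.

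Under SAP 5.1.1.1.4, early-withdrawal assessments that do not fall on a scheduled visit are "assigned to the next scheduled site visit per the protocol following the last visit where assessments were available". If the assessment is not scheduled at that visit, the data are listed but not tabulated. Otherwise "a mapped early withdrawal visit is considered as observed at that visit and should be summarized as such in the tables". The exemption is narrow: "The only exception to the above rule is for anti-bimekizumab antibody assessments".

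SAP 5.7.1.1 summarizes PK in the PK-PPS and has two date filters. The first: if "dosing for a visit is +/- 21 days out of window then the plasma concentration from that visit and all subsequent visits" are excluded. The second drops a sample drawn more than one day after the dosing date. All concentrations are listed. The summary table and figure are repeated by anti-drug antibody (ADAb) and neutralizing antibody (NAb) status.

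**The concern.** On-treatment samples are taken before dosing at 4-week intervals, so on schedule each Week 4 to 16 value lies about 28 days after a dose. A mapped PEOT value need not. It can be drawn a few days after a dose, or well beyond 28 days if a visit was missed, and still carry the next visit's label. It then enters the geometric mean, CV and concentration-time curve for that visit.

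The SAP recognises elsewhere that timing matters. It bars a Baseline plasma concentration drawn after the first dose (5.1.1.1.5), and it ties by-visit ADAb results to within 14 days of the dosing visit (5.7.1.4). At stake is how far the by-visit PK summaries of a study with 30 planned bimekizumab participants can be read as values at a known point in the dosing interval, above all in small antibody-status subgroups.

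**Working it through.** The plan gives no PK figure to reproduce. The check follows the rules and then sizes the effect.

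**1. Where a PEOT sample lands**

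| Last visit with data | Mapped to | PK drawn there? | Result |
|---|---|---|---|
| Baseline | Week 1 | No | Listed only |
| Week 1 | Week 2 | No | Listed only |
| Week 2 | Week 4 | Yes | Summarized |
| Week 4 | Week 8 | Yes | Summarized |
| Week 8 | Week 12 | Yes | Summarized |
| Week 12 | Week 16 | Yes | Summarized |

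A PEOT sample 7 days after the Week 4 dose is summarized at Week 8. So is one 42 days after that dose if the Week 8 visit was missed.

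**2. Whether a filter removes it**

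- The 21-day filter tests the dosing at the visit. A PEOT visit has none.
- The one-day filter can only refer to the same visit's dose. Read against the previous dose, it would delete every sample from Week 4 to Week 16. It therefore does not reach PEOT samples either.
- The PK-PPS excludes participants with important deviations that affect the concentration. Stopping under the criteria in Protocol 7.1 and then attending PEOT follows the protocol, so exclusion need not result.

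**3. Size of one mapped value**

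The documents give no half-life. I assume 20 to 30 days and log-linear decline after the last dose, ignoring absorption. Ratio to the 28-day value = 2^((28 − t)/half-life).

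- t = 7: 2^(21/20) = 2.07; 2^(21/30) = 1.62.
- t = 42: 2^(−14/20) = 0.62; 2^(−14/30) = 0.72.

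One value among n multiplies the geometric mean by ratio^(1/n). For t = 7:

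- n = 30: 2.07^(1/30) = 1.025 (+2.5%); 1.62^(1/30) = 1.016 (+1.6%).
- n = 5 (an assumed subgroup size; 5.7.1.1 allows geometric means from n = 3): 2.07^(1/5) = 1.157 (about +16%); 1.62^(1/5) = 1.10 (about +10%).
- Three such values among 30: 2.07^(3/30) = 1.075 (about +7.5%).

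With half-lives from 14 to 35 days, the day-7 ratio runs from 2^(21/14) = 2.83 down to 2^(21/35) = 1.52. The shift at n = 30 then runs from 3.5% down to 1.4%.

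**4. What the 21-day limit permits**

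Counted from the nominal day, 28 ± 21 gives about 7 to 49 days since the previous dose. Counted beyond the ±3-day window, 28 ± 24 gives 4 to 52. The SAP does not say which count applies. Both ranges are upper bounds, because the PK-PPS may remove such participants first.

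**5. A check on time since dose**

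Two visits each off by up to 3 days give 28 ± 6, or 22 to 34 days. The ratios are then 2^(±6/20) = 0.81 to 1.23 and 2^(±6/30) = 0.87 to 1.15.

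**6. Why this check cannot replace the present exclusion**

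Suppose the Week 8 dose is not given and the Week 12 dose is. The Week 16 sample is 28 days after a dose and passes. Let r = 2^(−28/half-life). Four doses give r + r² + r³ + r⁴, and the missing dose removes r². The remaining fraction is 1 − r/(1 + r + r² + r³).

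- Half-life 20: r = 0.379, fraction 1 − 0.379/1.577 = 0.76.
- Half-life 30: r = 0.524, fraction 1 − 0.524/1.942 = 0.73.

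That value is 24% to 27% below the four-dose value, so excluding all subsequent visits does work that a time-since-dose check cannot.

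**The case against.** The strongest reply is that the PK-PPS is the main safeguard. Its deviation categories include incorrect dose, treatment noncompliance and procedural noncompliance, and the detailed criteria sit in a document that is not available here. This stands for mistimed doses: a dose far outside the ±3-day window may remove the participant before the 21-day limit matters. It does not answer the PEOT case, where the participant may have followed the protocol throughout.

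Three stronger readings are tempting, and the documents do not support them.

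- **Samples after a skipped dose are kept.** Protocol 7.1.3 says that "Doses of IMP that were missed due to a reasonable interfering AE or exceptional circumstance" do not make a participant noncompliant, but that says nothing about PK-PPS membership. The SAP is silent on a dose with no date. It does not say that such samples stay in.
- **Samples from 7 to 49 days will be in the summaries.** That is only what the 21-day rule alone would allow.
- **The plan presents these values as 4-week troughs.** Neither document uses the term. The values are summarized by nominal visit, and the 28-day meaning is inferred from the sampling schedule.

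It is also fair to say that PK is a tertiary, descriptive endpoint. All concentrations are listed, SAP 5.7.1.4 provides individual plots with dosing marks, and Protocol 9.4.2 allows separate model-based PK. Protocol 4.2 credits PK/PD comparability to a separate Phase 1 study. These points limit the consequence but leave the mapping as it is.

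**Conclusion.** The PEOT point holds on the wording of the SAP. Once Week 2 is the last visit with data, or any later visit is, a PEOT concentration that does not fall on a scheduled visit is tabulated as the next visit's value with no regard to time since dose, and no stated filter reliably removes it. For mistimed or missed doses the finding is weaker: the 21-day limit is wide and ambiguously counted, and the SAP has no rule for a dose that was not given.

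The effect is small overall and larger in small antibody-status subgroups. The percentages in the working rest on an assumed half-life, log-linear decline and an assumed number of affected participants. The effect on the CV is not quantified, since the documents give no between-participant variance. The co-primary analyses are untouched.

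**What to change.** - **SAP 5.1.1.1.4:** add PK as a second exception. A PEOT concentration outside the window of the scheduled PK visit to which it would be mapped is listed and shown in the individual plots, but not mapped into by-visit summaries.
- **SAP 5.7.1.1, existing rule:** keep the exclusion of the affected visit and all subsequent visits, and state that it also applies after a dose that was not given. State whether the 21 days run from the nominal day or the window edge, and that the dosing date in the one-day filter is that of the same visit.
- **SAP 5.7.1.1, added check:** include a Week 4 to 16 concentration in by-visit summaries only if the time since the preceding dose lies within a stated margin tied to the ±3-day windows, for example 22 to 34 days. This supplements the existing exclusion and does not replace it.

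The cost is SAP wording and programming from dosing and sampling dates already collected. SAP 5.7.2 already requires time since the previous dose for the NAb listing. A few values leave the summaries but remain in the listings.

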5.1.1.1.5 Definition of Baseline values

A Baseline value for clinical variables is defined as the latest measurement on or prior to the first dosing day of study medication, regardless of the time of the measurement, for the Treatment Period. If a Baseline assessment is taken on the same day as first administration of study medication, it is eligible to be used as the Baseline value, even in the case that the time of the assessment is recorded as taking place after the time of first study medication administration. One exception to this rule is plasma concentration. If Baseline plasma concentration is measured at a time after the first administration of study medication, then it will not be eligible to be considered as a Baseline plasma concentration. Such cases will be discussed with the quantitative clinical pharmacologist.

If a Baseline measurement is missing or not collected, and a Screening value is available, the Screening value will be utilized as Baseline instead. If no measurement is available prior to receiving study medication, then the Baseline value is treated as missing.

Baseline values for component scores should be computed using components from the same visit where the relevant measurements were recorded prior to dosing. For example, if the Screening visit has all of the components, but the Baseline visit is missing one or more components, the Baseline value for the component score should be calculated using the Screening visit values.

5.1.1.2 Protocol Deviations

Important protocol deviations are deviations from the protocol which potentially could have a meaningful impact on study conduct, or on the primary efficacy, key safety, or other PK outcomes for an individual participant. The criteria for identifying important protocol deviations will be defined within the appropriate protocol-specific document at study start. Important protocol deviations will be reviewed as part of the ongoing data cleaning process and all important deviations will be identified and documented to confirm exclusion from analysis sets

5.1.1.3 Treatment assignment and treatment groups

It is expected that study participants receive treatment as randomized and hence safety analyses will be based on the SS, as randomized. However, if after unblinding it is determined that study participants randomized to placebo received bimekizumab at any time, then for safety analyses these study participants will be reallocated to the appropriate bimekizumab treatment group, unless otherwise specified. Study participants randomized to bimekizumab will only be reallocated to the placebo group if they never received bimekizumab.

Efficacy analyses should be performed according to randomized treatment and not actual Port any aria treatment received.

Center pooling strategy 5.1.1.4

No pooling of centers is planned for this study.

Coding dictionaries 5.1.1.5

Medical history and AEs will be coded using the Medical Dictionary for Regulatory Activities (MedDRA®). Medications will be coded using the World Health Organization Drug Dictionary (WHO-DD). Medical procedures will not be coded.

For MedDRA, version 19.0 or later will be used. For WHO-DD, version Mar/2021 or later will be used.

Multicenter studies 5.1.1.6

The data from all centers will be pooled for the purposes of the analysis. No exploration of treatment by center interaction will be investigated.

5.1.1.7 Handling of dropouts or missing data

Details about approaches to handle missing data are described in this section.

Efficacy missing data 5.1.1.7.4

An intercurrent event is defined as discontinuation of IMP prior to Week 16.

For study participants who experience an intercurrent event, the intercurrent event date is defined as:

Last study treatment date + 28 days (dosing interval) + 3 days (visit window)

For both co-primary endpoints (PASI90 and IGA 0/1 at Week 16), participants with an intercurrent event will be considered as nonresponder.

For secondary efficacy binary endpoints (PASI100 response at Week 16, IGA 0 response at Week 16, PSD [P-SIM] [itch, pain, and scaling] response at Week 16, Scalp IGA 0/1 response at Week 16, and DLQI 0/1 response at Week 16), study participants with intercurrent event will be handled using the same approach as the co-primary endpoints.

For PASI75 response at Week 4, a study participant will be considered a nonresponder only if the intercurrent event date occurs prior to the date of the Week 4 assessment.

Any missing data for the primary and secondary binary endpoints not associated with discontinuation of IMP will also be imputed as a nonresponse.

For the secondary continuous endpoint (percent change from baseline in BSA affected by PSO), participants with an intercurrent event are treated as though they had completed the randomized study treatment through Week 16 by imputing data following an intercurrent event using LOCF (see section 5.4.1.2.2). In addition, missing data not associated with discontinuation of IMP will also be imputed using LOCF.

For all tertiary endpoints, all data collected after an intercurrent event will be treated as missing and subject to imputation as described in section 5.5.

